8.1 Potential Risks

MgSO₄ IV infusion: The AEs associated with parenterally administered magnesium are usually concentration dependent. Magnesium acts peripherally to cause vasodilation. At low doses, it causes flushing and sweating, while at higher doses, it may cause hypermagnesemia and hypotension, depressed reflexes, flaccid paralysis, hypothermia, circulatory collapse, cardiac and central nervous system depression proceeding to respiratory paralysis. The dose (30 mg/kg/day) selected for the current study is intended to prevent serum concentrations >2 mmol/L, a threshold associated with the onset of AEs. Elevations in Alanine Aminotransferase and Aspartate Aminotransferase have been seen with the administration of IV magnesium.

This product contains aluminum that may be toxic. Aluminum may reach toxic levels with prolonged parenteral administration, if kidney function is impaired. Individuals with renal impairment are not eligible to participate in this study.

Magnesium concentration-dependent toxicity, defined as SMCs >2.1 mmol/L (>5 mg/dL) are associated with decreased deep-tendon reflexes, flushing, and somnolence. Serum magnesium concentrations >4.9 mmol/L (>12 mg/dL) are associated with respiratory paralysis and heart block. Magnesium concentrations will be closely monitored in this study.

Oral magnesium L-threonate: Oral magnesium products are typically well tolerated. The most common AEs are diarrhea and nausea, which are typically dose dependent. Dosing in the current study will be based on weight. If dose-limiting AEs occur, patients will be maintained on the highest tolerated dose. Elevations in Alanine Aminotransferase and Aspartate Aminotransferase have been seen with the administration of oral magnesium.

Phlebotomy: may be associated with discomfort, bruising, local hematoma formation and, on rare occasions, infections, lightheadedness, and fainting. The amount of blood drawn for research purposes will be within the limits allowed for adult or pediatric subjects by the NIH CC (Medical Administrative Policy 95-9: Guidelines for Limits of Blood Drawn for Research Purposes in the Clinical Center).

Venous line placement: Venous catheter insertion is associated with bruising, infection, or clot formation. Using proper placement techniques will minimize these risks.

CT scan: These scans are commonly used to monitor lymphoproliferative disease. Adverse reactions to iodinated contrast agent are typically mild and include metallic taste in the mouth, coldness in the arm during/after injection, headache, and nausea. These minor side effects occur in less than 3% of patients. More severe reactions, though extremely rare, include allergic reaction, shortness of breath, wheezing, flushing, hives, and decrease in blood pressure. Severe reactions including hypotensive collapse, shock, and death are reported in less than 1 in 40,000 patients. Iodinated contrast should not be used in participants who have undergone a renal transplant or who have been classified as Stage IV-V renal failure.

This research study involves exposure to radiation from 1 CT scan. Participants will be exposed to a maximum radiation amount of 1.2 rem, which is within the safety limit of 5 rem for adults, but is higher than 0.5 rem per year dose guideline for children set by the NIH Radiation Safety Committee. If participants would like more information about radiation and examples of exposure levels from other sources, they may ask the investigator for a copy of the pamphlet "An Introduction to Radiation for NIH Research Subjects."

New diagnoses: It is possible that the standard medical tests performed as part of this research protocol will result in new diagnoses. Depending on the medical findings and their implications, this could be viewed by study participants as either as a risk or a benefit. There is an additional risk that testing associated with clinical laboratory, or research laboratory testing, may lead to the identification of new medical diagnoses, or the potential for certain diseases to develop in the future. Any such information will be shared and discussed with the subject, and, if requested by the subject, it will be forwarded to the subject's primary health care provider for further evaluation and management.

8.2 Potential Benefits

Patients may derive no direct benefit from participating in this study. All patients will receive magnesium supplementation, and if magnesium is effective, they may derive benefit from improved NK and CD8 T cell functions and NKG2D expression, and, in some patients, accompanying reductions in EBV load. There may be some benefit associated with the close follow-up and additional monitoring inherent to participation in this study.

9 Research Use of Stored Human Samples, Specimens or Data

Intended use: The blood samples and data collected under this protocol may be used to study XMEN syndrome. No genetic testing will be performed. For any other research or experimental treatments done under this or other protocols, a separate informed consent will be obtained.

Storage: Access to stored samples will be limited using either a locked room or a locked freezer. Samples and data will be stored using codes assigned by the study investigators. Data will be kept in password-protected computers. Only investigators will have access to the samples and data.

Tracking: Samples and data will be tracked by use of the Biological Specimen Inventory (BSI) software (by Information Management Services, Inc.).

Disposition at the completion of the protocol:

- In the future, other investigators (both at NIH and outside) may wish to study these samples and/or data. In that case, IRB approval must be sought prior to sharing any of samples and/or data. Any clinical information shared about the sample would similarly require prior IRB approval.
- At the completion of the protocol (termination), samples and data will either be destroyed, or after IRB approval, transferred to another existing protocol.

Reporting the loss or destruction of samples/specimens/data to the IRB:

- Any loss or unanticipated destruction of samples or data (for example, due to freezer malfunction) that meets the definition of a protocol deviation and/or compromises the scientific integrity of the data collected for the study; will be reported to the NIAID IRB.
- Additionally, patients may decide at any point not to have their samples stored. In this case, the principal investigator will destroy all known remaining samples and report what was done both to the subject and to the IRB. This decision will not affect the subject's participation in other protocols at NIH.

10 Assessment of Safety

10.1 Recording/Documentation

At each contact with the subject, information regarding AEs will be elicited by appropriate questioning and examinations. All events, both expected/unexpected and related/unrelated will be recorded on a source document. Source documents will include: progress notes, laboratory reports, consult notes, phone call summaries, survey tools and data collection tools. Source documents will be reviewed in a timely manner by the research team. All reportable AEs that are identified will be recorded in CRIMSON. The start date, the stop date, the severity of each reportable event, and the PI's judgment of the AE's relationship and expectedness to the study agent/intervention will also be recorded in CRIMSON.

10.2 Definitions

Adverse Event (AE)

An adverse event is any untoward or unfavorable medical occurrence in a human subject, including any abnormal sign (e.g., abnormal physical exam or laboratory finding), symptom, or disease, temporally associated with the subject's participation in the research, whether or not considered related to the research.

Serious Adverse Event (SAE)

A Serious Adverse Event is an AE that results in one or more of the following outcomes:

- death
- a life threatening (i.e., an immediate threat to life) event
- an inpatient hospitalization or prolongation of an existing hospitalization
- a persistent or significant incapacity or substantial disruption of the ability to conduct normal life functions
- a congenital anomaly/birth defect
- a medically important event*

Medical and scientific judgment should be exercised in deciding whether expedited reporting is appropriate in other situations, such as important medical events that may not be immediately life

threatening or result in death or hospitalization but they may jeopardize the subject or may require intervention to prevent one of the other outcomes listed above.

Unexpected Adverse Event

An AE is unexpected if it is not listed in the Package Insert or is not listed at the specificity or severity that has been observed.

Unanticipated Problem (UP)

An Unanticipated Problem is any event, incident, experience, or outcome that is

1. unexpected in terms of nature, severity, or frequency in relation to
 - a. the research risks that are described in the IRB-approved research protocol and informed consent document; package insert or other study documents; and
 - b. the characteristics of the subject population being studied; and
2. possibly, probably, or definitely related to participation in the research; and
3. places subjects or others at a greater risk of harm (including physical, psychological, economic, or social harm) than was previously known or recognized.

Unanticipated Problem that is not an Adverse Event (UPnonAE)

Unanticipated problem that is not an Adverse Event (UPnonAE): An unanticipated problem that does not fit the definition of an adverse event, but which may, in the opinion of the investigator, involve risk to the subject, affect others in the research study, or significantly impact the integrity of research data. Such events would be considered a non-serious UP. For example, we will report occurrences of breaches of confidentiality, accidental destruction of study records, or unaccounted-for study drug

Serious Unanticipated Problem: A UP that meets the definition of an SAE or compromises the safety, welfare, or rights of subjects or others

Protocol Deviation: Any change, divergence, or departure from the IRB approved study procedures in a research protocol. Protocol deviations are designated as serious or non-serious and further characterized as

1. Those that occur because a member of the research team deviates from the protocol.
2. Those that are identified before they occur, but cannot be prevented.
3. Those that are discovered after they occur

Serious Protocol Deviation: A deviation that meets the definition of a Serious Adverse Event or compromises the safety, welfare or rights of subjects or others.

Non-compliance: The failure to comply with applicable NIH HRPP policies, IRB requirements, or regulatory requirements for the protection of human subjects. Non-compliance is further characterized as

1. Serious: Non-compliance that
 - a. Increases risks, or causes harm, to participants
 - b. Decreases potential benefits to participants
 - c. Compromises the integrity of the NIH-HRPP
 - d. Invalidates the study data
2. Continuing: Non-compliance that is recurring
3. Minor: Non-compliance that is neither serious nor continuing.

10.3 Investigator Assessment of Adverse Events

If a diagnosis is clinically evident (or subsequently determined), the diagnosis rather than the individual signs and symptoms or lab abnormalities will be recorded as the AE.

All AEs thought to be related to magnesium therapy or study procedures occurring from the time the informed consent is signed through the final study visit will be documented, recorded, and reported.

The Investigator will evaluate all AEs with respect to **Seriousness** (criteria listed above), **Severity** (intensity or grade), and **Causality** (relationship to study agent and relationship to research) according to the following guidelines.

10.3.1 Severity

The Common Terminology Criteria for Adverse Events (v 4.0) will be used to evaluate the severity of AEs: http://ctep.cancer.gov/protocolDevelopment/electronic_applications/ctc.htm

10.3.2 Causality

Causality (likelihood that the event is related to the study agent) will be assessed considering the factors listed under the following categories:

Definitely Related

- reasonable temporal relationship
- follows a known response pattern
- clear evidence to suggest a causal relationship
- there is no alternative etiology

Probably Related

- reasonable temporal relationship
- follows a suspected response pattern (based on similar agents)
- no evidence of a more likely alternative etiology

Possibly Related

- reasonable temporal relationship
- little evidence for a more likely alternative etiology

Unlikely Related

- does not have a reasonable temporal relationship
OR
- good evidence for a more likely alternative etiology

Not Related

- does not have a temporal relationship
OR
- definitely due to an alternative etiology

Note: Other factors (e.g., dechallenge, rechallenge) should also be considered for each causality category when appropriate. Causality assessment is based on

available information at the time of the assessment of the AE. The investigator may revise the causality assessment as additional information becomes available.

10.4 Reporting Procedures to the NIAID IRB

10.4.1 Expedited Reporting to the NIAID IRB

Serious and non-serious UPs, deaths, serious deviations, and serious or continuing non-compliance will be reported within 7 calendar days of investigator awareness. SAEs that are possibly, probably, or definitely related to the research will be reported to the NIAID IRB within 7 calendar days of investigator's awareness, regardless of expectedness.

10.4.2 Waiver of Reporting Anticipated Protocol Deviations, Expected UPnonAEs and Deaths to the NIAID IRB

Anticipated deviations in the conduct of the protocol will not be reported to the IRB unless they occur at a rate greater than anticipated by the study team. We expect up to 10% of doses to have been missed based on medication review at each visit; accordingly, we will only report missed doses as deviations if more than 20% are missed.

Expected AEs will not be reported to the IRB unless they occur at a rate greater than that known to occur in XMEN syndrome. If the rate of these events exceeds the rate expected by the study team, the events will be classified and reported as though they are unanticipated problems.

Deaths related to the natural history of XMEN syndrome will be reported at the time of continuing review.

10.4.3 Annual Reporting to the NIAID IRB

The following items will be reported to the NIAID IRB in summary at the time of Continuing Review:

- Serious and non-serious unanticipated problems
- Expected serious adverse events that are possibly, probably, or definitely related to the research
- Serious adverse events that are not related to the research
- All adverse events, except expected AEs granted a waiver of reporting.
- Serious and Non-Serious Protocol deviations
- Serious, continuing, and minor non-compliance
- Any trends or events which in the opinion of the investigator should be reported

10.5 Follow-Up of Adverse Events and Serious Adverse Events

AEs that occur following enrollment of the subject (by signing the informed consent) are followed until the final outcome is known or until the end of the study.

SAEs that have not resolved by the end of the study are followed until final outcome is known. If it is not possible to obtain a final outcome for an SAE (e.g., the subject is lost to follow-up), the reason a final outcome could not be obtained will be recorded by the investigator on the SAE/UP report form.

SAEs that occur after 50 weeks of study that are reported to and are assessed by the Investigator to be possibly, probably, or definitely related must be reported to the IRB, as described above.

10.6 Halting Criteria for the Protocol

Halting the study requires immediate discontinuation of study agent administered for all subjects and suspension of enrollment until a decision is made whether or not to continue study agent administration. If 2 or more subjects experience the same or similar AE of Grade 3 or above that is thought to be related to the magnesium supplementation, the study will be halted for review of the event(s) and re-evaluation of study risks, safety measures, and possible modification of the protocol and consent as may be appropriate, and for not less than 2 weeks. The IRB or DSMB may halt the study at any time following review of any safety concerns.

The IRB or NIAID, as part of their duties to ensure that research subjects are protected, may discontinue the study at any time. Subsequent review of serious, unexpected and related AEs by the DSMB or IRB may also result in suspension of further trial interventions/administration of study agent.

10.6.1 Reporting of Study Halting

If a halting requirement is met, a description of the event(s) or safety issue must be reported by the PI within one business day to the IRB and DSMB.

10.6.2 Resumption of a Halted Study

The DSMB, in collaboration with the PI will determine if it is safe to resume the study.

10.7 Pausing Criteria for a Subject

The decision to suspend administration of the study agent(s) for a single subject requires discontinuation of study agent administered for the study subject until a decision is made whether or not to continue study agent administration.

The pausing criteria for a single subject in this study include:

- A subject experiences an SAE or any Grade 3 or greater AE that is unexpected and is possibly, probably, or definitely related to the study agent;
OR

Any safety issue that the PI determines should pause administration of the study agent to a single subject.

IV magnesium would be stopped for a subject who experienced any of the following:

- “Abnormal” EKG values, as determined by the cardiologist on the study staff
- Development of advanced heart block
- Widening of QRS of more than 20 msec into the abnormal range (>110 msec) or more than 10 msec with QRS >120 msec
- Symptomatic hypotension
- Unexplained syncope

10.7.1 Reporting of Pausing for a Subject

If a pausing requirement is met, a description of the AEs or safety issue must be reported by the PI by fax or email within one business day to the IRB.

10.7.2 Resumption of a Paused Study

The DSMB, in collaboration with the PI will determine if it is safe to resume administration of the study agent to the subject. Any EKG abnormality will be assessed by a cardiologist to determine whether it would be safe to resume treatment. Grade 3 AEs that are thought to be related to the study medication must return to at least grade 1 before continuing with treatment.

10.8 Withdrawal Criteria for an Individual Subject

An individual subject will be withdrawn for any of the following:

- An individual subject's decision.
(The Investigator should attempt to determine the reason for the subject's decision.)
- Any clinical AE, laboratory abnormality or other medical condition or situation such that continued participation in the study would not be in the best interest of the subject. Subjects will be followed for the duration of the study for indicated safety assessments.
- Non-compliance with study procedures to the extent that it is potentially harmful to the subject or to the integrity of the study data.

10.9 Replacement for Withdrawn Subjects

Withdrawn subjects may be replaced if eligible replacements can be identified.

11 Remuneration Plan

Eligible subjects will be compensated for travel according to the NIAID/NIH travel policy. Subjects will receive financial compensation for the time and inconvenience of study participation according to the NIH CC volunteer guidelines at \$10 per inconvenience unit (IU). Total compensation will be \$720 (completion of Part I only) or \$1365 (completion of Part I and Part II). See Appendix D for detailed compensation amounts. Subjects will be compensated at the completion of part I, part II, or at time of withdrawal from the study (for portion of study completed).

12 Clinical Monitoring Structure

12.1 Site Monitoring Plan

As per International Conference on Harmonization (ICH)-Good Clinical Practice (GCP) 5.18, clinical protocols are required to be adequately monitored by the study sponsor. This study monitoring will be conducted according to the "NIAID Intramural Clinical Monitoring Guidelines." Monitors under contract to the NIAID Office of Clinical Research Policy and Regulatory Operations (OCRPRO) will visit the clinical research site to monitor several aspects of the study in accordance with the appropriate regulations and the approved protocol. Only pediatric subjects will be monitored and the objectives of a monitoring visit will be: 1) to verify the existence of signed informed consent documents and documentation of the informed consent process for each monitored pediatric subject; 2) to verify AEs and SAEs, including the prompt reporting of all SAEs; 3) to compare applicable CRIMSON data abstracts with individual subjects' records and source documents (subjects' charts, laboratory analyses and test results, physicians' progress notes, nurses' notes, and any other relevant original subject information); and 4) to help ensure investigators' are in compliance with the protocol.

The investigator (and/or designee) will make study documents (e.g., consent forms, CRIMSON data abstracts) and pertinent hospital or clinical records readily available for inspection by the local IRB, the site monitors, and the NIAID staff for confirmation of the study data.

A specific protocol monitoring plan will be discussed with the principal investigator and study staff prior to enrollment. The plan will outline the frequency of the monitoring visits based on factors such as study enrollment, data collection status, and regulatory obligations.

12.2 Data and Safety Monitoring Board

The NIAID Intramural Data and Safety Monitoring Board (DSMB) will review the study prior to initiation and twice a year thereafter. The Board may convene additional reviews as necessary. The Board will review the study data to evaluate the safety, efficacy, study progress, and conduct of the study. All SAE and UP will be reported by the PI to the DSMB at the same time they are submitted to the IRB. The PI will notify the DSMB of any cases of intentional or unintentional unblinding as soon as possible. The PI will notify the Board at the time pausing or halting criteria are met and obtain a recommendation concerning continuation, modification, or termination of the study. The PI will submit the written DSMB summary reports with recommendations to the IRB upon receipt.

13 Statistical Considerations

13.1 Study Hypotheses

Cohort 1: The absolute numbers of EBV-infected B cells in XMEN subjects with a blood EBV viral load $\geq 5,000$ copies/mL or EBV log ≥ 3.7 IU/mL will be lower following treatment with IV MgSO₄ and oral magnesium L-threonate than following placebo administration.

Cohort 2: The surface expression of NKG2D in XMEN subjects with baseline blood EBV viral load $< 5,000$ copies/mL or EBV log < 3.7 IU/mL will be greater following treatment with IV MgSO₄ and oral magnesium L-threonate than following placebo administration.

Treatment with IV MgSO₄ and oral magnesium L-threonate will increase the intracellular free Mg²⁺ level without increasing serum Mg²⁺ to supraphysiologic levels leading to improvement in NK and CD8 T cell functions and NKG2D expression in subjects with XMEN, thereby reducing the number of EBV-infected B cells.

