The proposed study has 2 parts, and patients will be divided into 2 cohorts. Patients in cohort 1 (high EBV group) will have baseline blood EBV viral load \geq 5,000 copies/mL or EBV log \geq 3.7 IU/mL. Patients in cohort 2 (low/no EBV group) will have baseline blood EBV viral load $<$ 5,000 copies/mL or EBV log $<$ 3.7 IU/mL. Part I is a randomized, double-blind, placebo-controlled, crossover study to evaluate the safety and efficacy of oral magnesium L-threonate in patients with XMEN syndrome. Within each cohort, patients will be randomized to receive escalating doses of either placebo or oral magnesium L-threonate for 12 weeks. Patients will then receive the crossover treatment (magnesium or placebo) for an additional 12 weeks. For patients who experience a 0.5-log decrease in the number of EBV-infected B cells (cohort 1) or a \geq 2-fold increase in NKG2D receptor expression on CD8 T cells (cohort 2) with oral magnesium as compared to placebo, the study will be complete. Patients who do not meet this efficacy outcome will undergo a 2-week washout period and proceed to Part II, an open-label, non-randomized evaluation of intravenous magnesium sulfate ($MgSO_4$) followed by oral magnesium L-threonate. These patients will be hospitalized to receive 3 days of intravenous $MgSO_4$ in 3 daily doses totaling 30 mg/kg/day. They will then restart escalating doses of oral magnesium L-threonate and continue for the remaining 24 weeks of Part II. If conducted, Part II will allow for secondary analyses to compare different durations of magnesium supplementation.

1 Background Information and Scientific Rationale

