2.2 Secondary Objectives

- To assess the safety and tolerability of MgSO₄ IV infusion and oral magnesium L-threonate.
- To evaluate the effects of magnesium supplementation on intracellular free Mg²⁺ concentrations in peripheral blood T cell lymphocytes.
- Contingent upon patient participation in Part II, to study the effect of 12 weeks vs. 24 weeks of oral magnesium supplementation after 3 days of IV magnesium on EBV viral load and number (or percent) of EBV-infected B cells (cohort 1) or NKG2D receptor expression on CD8 T cells (cohort 2) in patients with XMEN syndrome.
- To evaluate the difference in NKG2D expression between patients with high EBV titers and patients with low or negative titers.

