3.2 Study Endpoints

Primary Endpoints

- Cohort 1: Difference between the absolute number of EBV-infected B cells (by EBV FISH) after 12 weeks of oral magnesium supplementation and after 12 weeks of placebo.
- Cohort 2: Difference between NKG2D expression in CD8 T cells after 12 weeks of oral magnesium supplementation and after 12 weeks of placebo.

Secondary Endpoints

- Incidence and severity of AEs throughout the study.
- Contingent upon patient participation in Part II, differences in EBV viral load and number (or percent) of EBV-infected B cells (cohort 1) or NKG2D expression in CD8 T cells (cohort 2) by duration (12 weeks of IV+oral versus 24 weeks of IV+oral) of magnesium supplementation regimen.
- Change in the intracellular pool of free Mg²⁺ by duration of magnesium supplementation regimen.
- Change in NKG2D expression in cohorts 1 and 2.

Exploratory Endpoints

- Change in CD4 T cell counts, B cell counts (or percent), and/or in NKG2D expression on NK (CD3-CD56+) cells.
- Quantification of EBV-infected B cells as determined by flow cytometry and FISH.
- Percent of anemia, neutropenia, thrombocytopenia, and abnormal liver enzymes.
- Difference in number and severity of infections between placebo and magnesium treatment periods.
- Difference in number of health-related days of missed school/work between placebo and magnesium treatment periods.
- Difference in number of emergency room visits and hospital admissions between placebo and magnesium treatment periods.

4 Study Population

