To determine which participants will continue to Part II, we will evaluate the MFI for NKG2D in CD8+ T cells in each patient after 12 weeks of oral magnesium and after 12 week of placebo. If a patient has a 2-fold or greater increase with oral magnesium as compared with placebo, then that patient's study participation will end. Those patients who do not meet this outcome will proceed to Part II (IV magnesium). Participation in Part II will depend on the result for each individual patient.

Contingent upon patient participation in Part II, secondary analysis will compare the MFI for NKG2D on CD8+ T cells at the end of 12 weeks versus 24 weeks of oral supplementation.

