13.5 Secondary Analyses

To compare the effect of IV magnesium followed by 12 weeks vs. 24 weeks of oral magnesium, we will calculate the difference between the number of EBV-infected cells (cohort 1) and NKG2D expression in CD8+ T cells (cohort 2) at 12 weeks to 24 weeks in Part II. We will also calculate the difference in NKG2D expression between the 2 cohorts at the same timepoints.

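### Intracellular free Mg²⁺, the first link in the section 13.1 mechanism, has no analysis in section 13, and its secondary endpoint names no placebo comparison

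*Combined protocol and SAP*

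**What the plan says.** The third paragraph of section 13.1 sets out a causal chain that begins with free Mg²⁺ and runs through NK and CD8 T cell function and NKG2D to EBV-infected B cells. Its first step is: "Treatment with IV MgSO₄ and oral magnesium L-threonate will increase the intracellular free Mg²⁺ level without increasing serum Mg²⁺ to supraphysiologic levels".

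Section 2.2 sets a matching secondary objective: "To evaluate the effects of magnesium supplementation on intracellular free Mg²⁺ concentrations in peripheral blood T cell lymphocytes". The corresponding secondary endpoint, in section 3.2 and the Protocol Summary, is narrower: "Change in the intracellular pool of free Mg²⁺ by duration of magnesium supplementation regimen".

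The word duration is spelled out only in the preceding endpoint, which concerns EBV and NKG2D and depends on Part II participation: "by duration (12 weeks of IV+oral versus 24 weeks of IV+oral) of magnesium supplementation regimen". The free Mg²⁺ endpoint carries neither that definition nor that condition.

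Section 13.2 analyses EBV-infected B cells and NKG2D. Sections 13.3 and 13.4 power those two outcomes. Section 13.5 compares the same two at 12 and 24 weeks of Part II and closes with: "We will also calculate the difference in NKG2D expression between the 2 cohorts at the same timepoints". After 13.1, section 13 mentions neither intracellular nor serum Mg²⁺.

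The assay itself is scheduled throughout (sections 6.2 to 6.4 and Appendix B). Every Part I completer has seven values: baseline and Weeks 4, 8, 12, 16, 20 and 24. Part II entrants have six more.

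**The concern.** The section 2.2 objective asks what magnesium does to free Mg²⁺. Answering it requires a comparison with no magnesium, and the only contrast the plan words for this outcome does not contain one.

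The result matters most if the primary endpoints do not move. Free Mg²⁺ on magnesium versus placebo would then help to separate two explanations: oral magnesium did not raise the intracellular pool, or it did and nothing followed. If the primary endpoints do move, the same comparison supports or weakens the proposed mechanism. The preliminary observations in section 1.1 (four patients, no control) already report improved intracellular magnesium. What this trial can add is the blinded control.

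With no contrast named, the choice of comparison is left until the data are in.

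**Working it through.** **1. Coverage, for the outcomes in the 13.1 chain**

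| Outcome | Objective | Endpoint | Analysis in section 13 |
|---|---|---|---|
| EBV-infected B cells | 2.1, 2.2 | 3.2 | 13.2 to 13.5 |
| NKG2D on CD8 T cells | 2.1, 2.2 | 3.2 | 13.2 to 13.5 |
| Intracellular free Mg²⁺ | 2.2 | 3.2 | none |

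**2. What each candidate contrast estimates**

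Let m_w be mean free Mg²⁺ at study week w without any magnesium effect, and τ the effect after 12 weeks of oral magnesium. Take equal numbers per sequence, as the Table 3 column heading does.

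- *Weeks on treatment in Part I (end minus start of the magnesium period).* Arm 1 gives τ + (m₁₂ − m₀) and Arm 2 gives τ + (m₂₄ − m₁₂). The average is τ + (m₂₄ − m₀)/2, so any time trend stays in the estimate. A comparison among 4, 8 and 12 weeks on treatment shows the shape of the response, not whether there is one relative to placebo.
- *12 versus 24 weeks in Part II (Week 50 minus Week 38).* This gives (effect at 24 weeks − effect at 12 weeks) + (m₅₀ − m₃₈). An effect already complete by 12 weeks cancels out. The setting is also uncontrolled: patients who miss the Part I criterion "proceed to Part II, an open-label, non-randomized evaluation of intravenous magnesium sulfate".
- *End of magnesium minus end of placebo in Part I.* Arm 1 (Week 12 − Week 24) gives τ + (m₁₂ − m₂₄). Arm 2 (Week 24 − Week 12) gives τ + (m₂₄ − m₁₂). The average is τ.

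Only the third isolates τ. It assumes no carry-over to the end of Arm 1's placebo period, 12 weeks after magnesium stops. A carry-over of λ would make the average τ − λ/2. The primary analysis relies on the same assumption.

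**3. Power of the third contrast**

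Inputs: two-sided α = 0.05, paired t-test, and n = 10 with 1.15 SD at 90% power (section 13.3); n = 20 with 0.76 SD (Table 3, section 13.4). SD means the SD of the within-patient differences.

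Formula: power = 1 − F(t₀.₉₇₅,ₙ₋₁; n − 1, δ√n), where F is the noncentral t distribution function and δ is the difference in SD units. The opposite tail is negligible.

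Reproducing the plan's figures:

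- n = 10: δ√n = 1.15 × √10 = 3.637; critical value 2.262; power 0.898. The exact detectable difference at 90% is 1.155 SD.
- n = 20: δ√n = 0.76 × √20 = 3.399; critical value 2.093; power 0.897. The exact detectable difference at 90% is 0.764 SD.

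Both agree with the plan. Applied to free Mg²⁺:

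| Analysis set | 90% power | 80% power | 90% power, period term added (n − 2 df) |
|---|---|---|---|
| One cohort, n = 10 | 1.155 SD | 0.996 SD | 1.174 SD |
| Cohorts combined, n = 20 | 0.764 SD | 0.660 SD | 0.767 SD |

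A true difference of 0.76 SD has 90% power with the cohorts combined and 57% within one cohort, so the choice to combine should be made in advance. The documents give no SD for free Mg²⁺ differences, so these figures cannot be put into mM.

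**The case against.** The strongest defence is that this is a mechanistic secondary endpoint in a Phase 1/2 study of about 20 patients. The data are collected in both blinded periods, so the magnesium-placebo comparison remains available to anyone who wants it. Section 13.5 speaks only of calculating differences and proposes no significance test for a secondary outcome. That stands as a limit on severity. It does not supply the missing contrast, and an endpoint worded without placebo does not answer the section 2.2 objective.

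Four stronger readings are tempting, and the documents do not support them.

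- *The plan commits to an uninformative 12-versus-24-week test of free Mg²⁺.* That definition belongs to the EBV/NKG2D endpoint only. Duration may equally mean weeks on oral magnesium in Part I. Any power quoted for the Part II contrast would also need an assumed late effect that the documents do not give.
- *Error rates are inflated by drift or by many candidate contrasts.* The documents give no drift, and the plan does not propose to test a set of contrasts at 0.05. Such rates are not consequences of this plan.
- *The whole third hypothesis is unanalysed.* Its NKG2D and EBV-infected B cell parts have Part I analyses in 13.2.
- *Serum magnesium has no limits.* Sections 4.3, 5.4.2 and 8.1 give thresholds, and serum levels are scheduled throughout. What is missing is a statement of which level the word supraphysiologic refers to, which is editorial.

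Combining the cohorts is also a choice rather than a correction, since the plan analyses and powers each cohort separately.

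**Conclusion.** The point holds as a gap in the plan. One secondary objective, its endpoint and the first step of the 13.1 mechanism have no analysis, and the endpoint as worded contains no placebo comparison on either reading of duration. The conclusion rests on the text of sections 2.2, 3.2 and 13 and needs no assumed effect size.

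Its size is limited. The primary analyses, the sample size and entry to Part II do not change, and nothing is lost at data collection. The contrast that would answer the objective has 90% power for 0.76 SD with cohorts combined or 1.15 SD within a cohort. This assumes all planned patients complete both periods, sequences are balanced and no carry-over remains.

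One part cannot be repaired by analysis. The 13.1 statement concerns IV plus oral magnesium, which is given only in Part II, where there is no placebo. The randomised comparison speaks to oral magnesium alone.

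**What to change.** 1. In section 3.2 and the Protocol Summary, reword the endpoint as the difference in intracellular free Mg²⁺ between the end of the magnesium period and the end of the placebo period in Part I.
2. In section 13.5, add the matching analysis: the within-patient difference from the Week 12 and Week 24 values, paired t-test, mean difference with 95% confidence interval. State in advance whether the cohorts are combined or analysed separately, and name this as the analysis of the free Mg²⁺ hypothesis for oral magnesium.
3. Define duration for this outcome. Label by-duration and Part II changes as descriptive and uncontrolled, and note in 13.1 that the IV-plus-oral statement has no placebo comparison.
4. Editorial only: say which serum level supraphysiologic refers to; word the two cohort hypotheses in 13.1 to match the oral-versus-placebo contrast in 13.2; and correct the direction of the expected Cohort 2 difference in 13.2, since an increase in NKG2D makes treatment minus placebo positive.

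The cost is one paragraph in 13.5, one endpoint line in two places and short wording edits. No visit, assay or patient is added, and the primary analysis stays as it is.
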